3.3 Analysis populations

Intention to Treat population: this population includes all aSAH patients randomized except those who were a post-randomization exclusion, withdrew consent, or were lost to follow up.

Per Protocol Population: this population is the intention to treat population except those who had a protocol violation (as defined in 3.2).

The primary analysis of all outcomes will be conducted on the Intention to Treat population. A secondary, sensitivity analysis, on the Per Protocol population will also be conducted and reported separately, accompanied by a description of the population characteristics, in the supplement.

Section 4 – Trial Population

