5.1 Outcome Definition

Primary outcome:

- Our primary outcome is the proportion of patients with unfavorable neurologic outcome (defined as mRS score of \geq 4 – see Table 1) at 12 months.

*Table 1: The Modified Rankin Scale**

Score	Description
0	No symptoms at all
1	No significant disability despite symptoms; able to carry out all ADLs
2	Slight disability; unable to carry out previous activities, but able to look after own affairs with assistance
3	Moderate disability; requiring some help but walks without assistance

4	Moderately severe disability; unable to walk unassisted and unable to look after own bodily needs unassisted
5	Severe disability; bedridden, incontinent and requiring constant nursing care and attention
6	Dead

*modified from Washington University in St. Louis' Internet Stroke Center (www.strokecenter.org)

Secondary outcomes:

- Functional Independence Measure (FIM) at 12 months. The FIM is a validated tool consisting of 18 items that assesses 13 different motor and 5 cognitive tasks each measured on an 8-point scale (see Table 2). As we expect that death will not be affected by the intervention, deceased patients will be given the lowest score.²² It has demonstrated excellent consistency in inter-rater reliability and internal consistency specifically in neurologic disorder populations. It is easy to administer and is validated for use by telephone and via proxy respondents.

Table 2: the Functional Independence Measure**

I. Assessment Dimensions:		II. Scoring Criteria:		
1.	Eating	Score:	Description:	Category:
2.	Grooming	7	Complete independence	No Helper Required
3.	Bathing			
4.	Upper body dressing			
5.	Lower body dressing	6	Modified independence	No Helper Required
6.	Toileting			
7.	Bladder management	5	Supervision or setup	Helper - Modified Dependence
8.	Bowel management			
9.	Bed to chair transfer			
10.	Toilet transfer	4	Minimal contact assistance	Helper - Modified Dependence
11.	Shower transfer			
12.	Locomotion	3	Moderate assistance	Helper - Modified Dependence
13.	Stairs			
14.	Cognitive comprehension			
15.	Expression	2	Maximal assistance	Helper - Complete Dependence
16.	Social interaction			
17.	Problem solving			
18.	Memory	1	Total assistance	Helper - Complete Dependence
		0	Activity does not occur	

**modified from Rehabilitation Measures Database (www.rehabmeasures.org)

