- EuroQOL Quality of Life Scale 5-Dimension 5-Level (EQ-5D- 5L) (generic scale) questionnaire is conducted at 12 months. It consists of a short and simple 5-part questionnaire and a visual analogue scale (VAS). It may be self-administered,

completed by interview or via a proxy respondent, and is used to value and describe health states. The questionnaire data is reported as an index value - a continuous fractional outcome with boundaries between zero and one. Zero represents the worst health status and 1 the best. The EQ-VAS (visual analogue scale) is a self-administered visual scale in which respondents rate from 0 to 100 (worst and best state of health respectively) their perceived health-related quality of life at the time of response. In analyses including non-survivors, deceased patients will be given the lowest score.²²

- Death in hospital.
- Delayed Cerebral Ischemia (DCI): defined as an otherwise unexplained decrease in Glasgow Coma Scale score of ≥ 2 points or new focal neurological deficit for ≥ 1 hour.
- Radiographic vasospasm: defined as a reduction of cerebral artery diameter on digital subtraction angiography (classified as mild [0-33% reduction], moderate [34-66% reduction] or severe [67-100% reduction]) or by transcranial Doppler of the middle or anterior cerebral artery (classified as mild [mean flow velocity of ≥ 120 and < 160 cm/sec AND Lindegaard ratio ≥ 3], moderate [mean flow velocity of ≥ 160 and < 200 cm/sec AND Lindegaard ratio ≥ 3] or severe [mean flow velocity of ≥ 200 cm/sec AND Lindegaard ratio ≥ 3]). This is considered incident if it occurs after randomization.
- New Cerebral infarction: defined a new area of infarcted brain (not present) at time of randomization, as captured on routine cranial imaging (e.g., CT or MRI) during the initial hospitalization. It is characterized as related to DCI/vasospasm, to complications from securing the ruptured aneurysm or other/unknown.

Tertiary Outcomes:

- Lowest daily hemoglobin level over the first 21 days in hospital
- Proportion of patients receiving at least one RBC transfusion
- Median number of RBC units transfused
- Expected adverse events of the first 28 days in hospital
- Transfusion-related adverse events of the first 28 days in hospital
- need for and duration of invasive mechanical ventilation – defined as mechanical ventilation delivered via either endotracheal intubation or tracheostomy
- ICU length of stay
- Hospital length of stay

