5.2 Analysis Methods

Unless otherwise specified, all analyses will be completed on the intention to treat population (see section 3.3). Given the pragmatic nature of the trial, and possible variations in practice from centre to centre, randomization was stratified by centre. As such, all primary analyses are adjusted for centre and sex as aSAH predominantly affects females. In summary, unless stated otherwise below, all parametric analyses will be conducted using Generalized Linear Mixed Models (GLMM) with fixed effects for treatment and sex, and a random effect for centre. Non parametric median estimates will be conducted using quantile regressions adjusting for site and sex. A summary of the proposed analyses is presented in Table 4.

Primary Outcome:

Primary analysis:

- The main statistical analysis will be done on the intention to treat population with a binomial GLMM with log-link function and reported as a risk ratio with corresponding 95% confidence interval.

Secondary analysis:

- For the primary outcome a proportional odds analysis, will additionally be conducted. The proportional odds assumption will be tested using the Brant-Wald test at the alpha level of 5%.

Sensitivity analysis:

Sensitivity analysis of the primary outcome will be tested in 4 ways:

- Further adjusted with WFNS and age as additional fixed effects
- We chose dichotomized mRS scores as the results of the analysis are simple to understand and interpret, but the cut-off is arbitrarily chosen and information is lost by dichotomization. Therefore, we will repeat the primary analysis with unfavorable neurologic outcome defined as mRS ≥ 3 rather than ≥ 4 .
- Per protocol analysis (see section 3.3)
- Best case-worst case scenario. In this sensitivity analysis of the primary outcome, we will include randomized patients in which the primary outcome is missing – e.g. withdrawal or lost to follow-up. Patients who were randomized in error will be excluded. Two scenarios will be considered:
 - Best-case scenario: a favourable outcome will be imputed for those in the liberal transfusion strategy arm with missing primary outcome, and unfavourable outcome to those in the restrictive transfusion strategy arm with missing primary outcome.
 - Worst-case scenario: an unfavourable outcome will be imputed for those in the liberal transfusion strategy arm with missing primary outcome, and a favourable outcome to those in the restrictive transfusion strategy arm with missing primary outcome.

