Secondary Outcomes:

- The Functional Independence Measure as well as Motor and Cognition sub-scores will be analysed using a linear GLMM with an identity link function. The treatment effect will be reported as a mean difference with 95% CIs. In addition, the same analyses will be done however now excluding patients who are deceased.
- EQ-5D-5L Visual Analogue Scale will be analysed using a linear GLMM with an identity link function. The treatment effect will be report as a mean difference with 95% CIs. In addition, the same analyses will be done however now excluding patients who are deceased.
- Mortality in hospital will be analysed using a log-binomial GLMM and reported as a risk ratio with 95% CI.
- Mortality at 12 months will be analysed using a log-binomial GLMM and reported as a risk ratio with 95% CI.
- The number of patients with new cerebral infarction, DCI, and radiographic vasospasm, post randomization will be analysed using a log-binomial GLMM and reported as a risk ratio with 95% CI.

Tertiary Outcomes:

- Lowest daily hemoglobin level over the first 21 days in hospital will be presented graphically as means with 95% confidence intervals per group

- Proportion of patients receiving RBC transfusion with between group differences analysed using using a log-binomial GLMM
- Median number of RBC units transfused will be reported with interquartile ranges and presented as median difference with 95% CI using quantile regression analyses adjusting for site and sex.
- Proportion of patients with expected and transfusion-related adverse events will be reported with between group differences analysed using using a log-binomial GLMM adjusting for site and sex
- Duration of invasive mechanical ventilation will be reported as presented as median difference with 95% CI using quantile regression analyses adjusting for site and sex.
- ICU and Hospital Length of stay will also be described as medians with interquartile ranges and presented as median differences with 95% CI using quantile regression analyses adjusting for site and sex.

Pre-planned Subgroup Analyses:

We plan exploratory subgroup analyses for the primary outcome (as described above) in the following groups:

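### Ventilation time and ICU and hospital stay are compared as adjusted medians with no rule for in-hospital death, so an early death counts the same as early extubation or discharge (minor)

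*SAP*

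**What the plan says.** SAP 5.2, Tertiary Outcomes, gives the analysis of stay: "ICU and Hospital Length of stay will also be described as medians with interquartile ranges and presented as median differences", with 95% CIs from quantile regression adjusted for site and sex. For ventilation: "Duration of invasive mechanical ventilation will be reported as presented as median difference with 95% CI using quantile regression analyses", with the same adjustment. Table 4 repeats this, with a dash under sensitivity analyses for both rows and only the median with IQR under additional analyses.

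The population is the default: "Unless otherwise specified, all analyses will be completed on the intention to treat population". SAP 3.3 defines it: "this population includes all aSAH patients randomized except those who were a post-randomization exclusion, withdrew consent, or were lost to follow up". Death is not a reason for exclusion. SAP 5.1 lists ICU and hospital length of stay without a definition and defines ventilation only by route of delivery.

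Elsewhere the SAP does set a rule for death. For FIM: "As we expect that death will not be affected by the intervention, deceased patients will be given the lowest score". For the EQ-5D-5L and its visual analogue scale: "In analyses including non-survivors, deceased patients will be given the lowest score". For FIM and the visual analogue scale, SAP 5.2 then adds: "In addition, the same analyses will be done however now excluding patients who are deceased". The three durations have neither provision.

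**The concern.** Duration of ventilation or stay ends at extubation, discharge or death, whichever comes first. Without a rule, a patient who dies on day 5 and one who goes home on day 5 contribute the same value. Adjusting for site and sex does not separate them.

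Death is not rare here. Protocol section 5 cites 35% mortality for the disease (range 20-67%), although that figure is not specific to the trial's population. If one strategy prevents early deaths, it moves patients from short durations to typical survivor durations and raises its own median. That could be read as slower recovery or greater resource use. A real shortening among survivors could be masked in the same way.

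**Working it through.** The plan states no expected value for any of the three durations, so there is no figure to reproduce. The check has two parts: what the text implies, and how large the effect could be under stated assumptions.

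**1. Text.** The three durations are analysed in the intention-to-treat population (SAP 5.2). That population keeps deaths (SAP 3.3). No rule for death appears in SAP 5.1, SAP 5.2, Table 4 or the protocol. Hence a death enters with the days observed up to death.

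**2. Size.** Let p be in-hospital mortality in an arm, F_S the distribution of stay in survivors and F_D that in patients who die. The median m of all patients solves

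(1 - p) F_S(m) + p F_D(m) = 0.5.

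Assumptions, none of them from the documents:
- survivors: lognormal, median 24 days, log-SD 0.6, the same in both arms;
- deaths: lognormal, log-SD 0.7, median varied;
- mortality 30% restrictive, 22% liberal.

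With deaths' median 8 days:
- Restrictive: m = 18.58, since 0.70 × 0.335 + 0.30 × 0.886 = 0.50.
- Liberal: m = 20.15, since 0.78 × 0.385 + 0.22 × 0.907 = 0.50.
- Liberal minus restrictive: +1.6 days, with no change in any survivor.

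The result depends on when deaths occur:

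| Deaths' median stay (days) | Restrictive | Liberal | Difference |
|---|---|---|---|
| 8 | 18.6 | 20.1 | +1.6 |
| 16 | 21.6 | 22.2 | +0.7 |
| 20 | 22.9 | 23.2 | +0.3 |
| 24 | 24.0 | 24.0 | 0 |
| 30 | 25.5 | 25.1 | -0.4 |
| 36 | 26.7 | 25.9 | -0.8 |

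With mortality 25% versus 20% and deaths' median 8 days, the difference is +1.0 day (19.6 versus 20.5). At equal mortality the two arms have the same mixture, so the difference is exactly 0.

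Masking: at 30% versus 22% and deaths' median 8 days, suppose liberal-arm survivors truly stay 8% less (median 22.1 days). The medians are then 18.6 and 18.7, a difference of +0.1 day, and the benefit is not visible.

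**3. A second set of assumptions.** Log-SD 0.7 throughout; survivors' median 14 days (ICU) or 28 days (hospital); mortality pairs 20/15, 25/20, 30/20 and 35/25%. With deaths' median 5 to 12 days, the liberal arm's median is longer by 0.1 to 1.2 days (ICU) and 1.0 to 3.5 days (hospital). With deaths' median equal to survivors', the difference is 0. With deaths' median 1.5 times survivors', it is -0.3 to -1.3 days.

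**4. Deaths ranked worst.** If deaths are placed above the longest observed duration, the median solves (1 - p) F_S(m) = 0.5, that is, m = 24 × exp(0.6 × z) with z the normal quantile of 0.5/(1 - p).
- Restrictive: 0.5/0.70 = 0.714, z = 0.566, m = 33.7.
- Liberal: 0.5/0.78 = 0.641, z = 0.361, m = 29.8.
- Difference: -3.9 days, again with no change in any survivor. At 25% versus 20% it is -2.0 days.

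If liberal-arm survivors instead stayed 8% longer, the ranked medians would be 33.7 and 32.2, still 1.5 days shorter for the liberal arm.

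**The case against.** The strongest reply has four parts.

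- **The SAP's premise.** It expects no effect on death (SAP 5.1, FIM). Under that premise there is no between-arm distortion. The trial hypothesis concerns death and severe disability combined, so it could be met without a mortality difference. The assumed 8-point mortality gap is large beside the 10-point gap in the whole composite on which the trial is sized (40% to 30%). This stands, and it makes the concern conditional. It does not close the gap, because mortality is itself a secondary outcome and the premise is among the things the trial tests.
- **The contrast with FIM and the visual analogue scale.** Those are 12-month scores that a deceased patient does not have, so a value must be assigned. A stay is fully observed in a patient who dies, and the raw median is a legitimate description of days used. This stands as a reason to keep the planned analysis.
- **Existing safeguards.** The outcomes are tertiary, a p-value is reported only for the primary outcome (SAP 3.1), and in-hospital and 12-month mortality are reported as risk ratios with 95% CIs. Simulating the 30% versus 22% scenario with 370 per arm, unadjusted, gives a 95% half-width of about 2.6 days, so the 1.6-day shift lies inside it. This stands, and it sets the severity.
- **Worst rank has the opposite flaw.** It puts the mortality effect into the duration, as step 4 shows. This stands against making it the main analysis.

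A reader might go further and infer that the plan counts early death as a good result, or that a life-saving strategy would necessarily look worse. The documents support neither. The SAP nowhere calls a short stay favourable, and neither document gives stay lengths or times to death from which a direction could be fixed.

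**Conclusion.** The gap is real and its consequence conditional. As written, an in-hospital death contributes its observed days to all three medians, and nothing in the plan lets a reader tell early death from early recovery. A spurious lengthening in the arm with fewer deaths needs both a mortality difference and deaths that precede survivors' discharge or extubation. Under the assumptions used, it ranges from a few tenths of a day to about 1.2 days for ICU stay, and from about 1 to 3.5 days for hospital stay. It is zero at equal mortality or equal timing, and it reverses when deaths come late. All stay distributions and mortality pairs are assumptions. Severity is minor: the primary conclusion is untouched and the outcomes carry no p-values.

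**What to change.** Keep the planned site- and sex-adjusted median difference and label it as days used regardless of survival. Before database lock, add to SAP 5.2 and Table 4, for ventilation duration, ICU stay and hospital stay:

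- (a) a sensitivity quantile regression with in-hospital deaths ranked worse than the longest observed duration, labelled as a composite of death and duration;
- (b) medians (IQR) by arm, shown separately for hospital survivors and non-survivors, labelled as descriptive and conditional on survival.

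State that all of these are to be interpreted alongside in-hospital mortality. In (a), an arm's median does not depend on the value assigned to deaths while fewer than half of that arm die.

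The cost is a few sentences, one recode and some supplementary rows, with no new data. The downside is that the ranked analysis carries any mortality effect, which is why it should sit beside the planned analysis and not replace it.

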APPENDIX:

Figure 1: The SAHaRA Research Program:

A. Current proposed study (circled) in context of research program; B. SAHaRA Trial design

aSAH=aneurysmal subarachnoid hemorrhage, Hb=hemoglobin, mRS=modified Rankin Scale, RBC=red blood cell, RCT=randomized controlled trial

C. SAHaRA Trial outline

[figure not shown]

Table 2: Functional outcome measures:

A. Modified Rankin Scale

Score	Description
0	No symptoms at all
1	No significant disability despite symptoms; able to carry out all ADLs
2	Slight disability; unable to carry out previous activities, but able to look after own affairs with assistance
3	Moderate disability; requiring some help but walks without assistance
4	Moderately severe disability; unable to walk unassisted and unable to look after own bodily needs unassisted
5	Severe disability; bedridden, incontinent and requiring constant nursing care and attention
6	Dead

*modified from Washington University in St. Louis' Internet Stroke Center (www.strokecenter.org)

B. Functional Independence Measure**

I. Assessment Dimensions:		II. Scoring Criteria:		
		Score:	Description:	Category:
1.	Eating	7	Complete independence	No Helper Required
2.	Grooming			
3.	Bathing	6	Modified independence	
4.	Upper body dressing			
5.	Lower body dressing	5	Supervision or setup	Helper - Modified Dependence
6.	Toileting			
7.	Bladder management	4	Minimal contact assistance	
8.	Bowel management			
9.	Bed to chair transfer	3	Moderate assistance	
10.	Toilet transfer			
11.	Shower transfer	2	Maximal assistance	Helper - Complete Dependence
12.	Locomotion			
13.	Stairs	1	Total assistance	
14.	Cognitive comprehension			
15.	Expression	0	Activity does not occur	
16.	Social interaction			
17.	Problem solving			
18.	Memory			

**modified from Rehabilitation Measures Database (www.rehabmeasures.org)

Table 3: Important baseline characteristics and co-interventions to be prospectively logged:

A. Baseline characteristics (from time of enrolment and randomization)

Factor	Variable to capture
Age at enrolment	Age in years
Sex	Male or Female
Ethnicity	As patient identifies
Language	Preferred language
History of CAD, HTN	Present or not
SAH Clinical Severity	WFNS score
SAH radiographic Severity	Modified Fisher Scale Score
Hydrocephalus	Need for EVD
Aneurysm size and location	Size (mm), artery involved
Method aneurysm secured	Clip or coil or not secured
Presence of Delayed Cerebral Ischemia	Delayed cerebral ischemia/radiographic vasospasm *

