Presence of cerebral infarct	Cerebral infarct on pre-randomization imaging

CAD=coronary artery disease, EVD=external ventricular drain, HTN=hypertension, SAH=subarachnoid hemorrhage, WFNS=World Federation of Neurosurgeons, *radiographic vasospasm defined as a reduction of cerebral artery diameter on digital subtraction angiography and classified as mild (0-33% reduction), moderate (34-66% reduction) or severe (67-100% reduction) or by transcranial Doppler of the middle or anterior cerebral classified as mild (mean flow velocity of ≥ 120 and < 160 cm/sec AND Lindegaard ratio ≥ 3), moderate (mean flow velocity of ≥ 160 and < 200 cm/sec AND Lindegaard ratio ≥ 3) or severe (mean flow velocity of ≥ 200 cm/sec AND Lindegaard ratio ≥ 3), delayed cerebral ischemia requires a clinical neurologic deterioration (defined as an otherwise unexplained decrease in Glasgow Coma Scale score of ≥ 2 points or new focal neurological deficit for ≥ 2 hours (or ≥ 1 hour and initiation of therapy))

B. Co-Interventions to be prospectively logged

	Co-Intervention	Variable to capture	Operationalization
Delayed Cerebral Ischemia/radiographic vasospasm*	Prophylaxis	Hyperdynamic therapy (prior to diagnosis of DCI)	-use of vasopressors to drive a target MAP>65mmHg
			-use of IV fluid infusions or regular boluses over maintenance
			-use of IV fluids to target specific hematocrit
		Magnesium (prior to diagnosis of DCI)	-use of magnesium IV infusion
	Chemical vasodilators (prior to diagnosis of DCI)	-use of infusion of vasodilator (IV) or any IA use (eg: milrinone, papaverine, CCB etc)	
	Treatment	Hyperdynamic therapy (after diagnosis of DCI)	-same criteria as above
		Magnesium	-same criteria as above
		Mechanical vasodilation	-use of balloon angioplasty or stent
Chemical vasodilation		-use of infusion of vasodilator (IV) or any IA use (eg: milrinone, papaverine, CCB etc).	
Definitive Aneurysm Management (if completed post randomization)	Clip vs coil		
	Time to clip or coil		
Blood pressure management	-daily use of vasopressor	-used or not	
	-highest daily target MAP		
Fever/temperature regulation	-fever	-daily highest temperature	

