3.1 Confidence Intervals and P-values

The statistical uncertainty of all estimates will be expressed as two-sided 95% confidence intervals. Therefore, the analyses for an unfavorable neurologic outcome will be tested at a 0.05 level of significance. A p-value will only be reported for the primary outcome.

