4.3 Baseline Patient Characteristics

Baseline characteristics of randomized patients include (see Table 3): age; sex; ethnicity; comorbidities; history of intracranial bleed, ischemic stroke, cocaine use; smoking history; aneurysm and SAH characteristics/grade; status of aneurysm and securing technique, any prior RBC transfusion, presence of Delayed Cerebral Ischemia (DCI) or radiographic vasospasm (RV), presence of cerebral infarct (CI), and any cardiovascular vasopressor/inotropic therapy prior to randomization, and hemoglobin at randomization. Further characteristics may be included, and adjustments can be made to the report format to meet editorial guidelines.

Section 5 – Analysis

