- Age: ≤ 55 years versus >55 years-old. We hypothesize that a liberal transfusion strategy is more effective in those over the age of 55. SAH incidence increases with age, especially those >55 years (mean age), and increased age is associated with worse outcome.²³ Previous transfusion trigger trials have demonstrated less benefit of a liberal transfusion trigger in those less than age 55.¹³ This subgroup has been explored in other large SAH²⁴ and transfusion trigger trials¹³.
- Sex: female sex versus male sex. We hypothesize no treatment effect difference between male and female sex.
- Clinical condition at admission: using the World Federation of Neurological Surgeons Score. We hypothesize that a liberal transfusion strategy is more effective in those with worse clinical condition at presentation. Worse clinical grade at presentation is associated with anemia and unfavourable outcome.^{6,23}
- Radiographic grade at admission: using the modified Fisher Scale. We hypothesize that a liberal transfusion strategy is more effective in those with higher grades. Worse radiographic grade at presentation is associated with anemia and unfavourable outcome.^{6,11,23}
- Method of treatment of Aneurysm: neurosurgical (craniotomy) extravascular versus endovascular aneurysm intervention. We hypothesis that a liberal transfusion strategy is more effective in those with extravascular interventions. Neurosurgical (craniotomy) management of ruptured aneurysms is associated with worse anemia and has greater morbidity.^{11,17}
- Baseline DCI: present at randomization vs not. We hypothesize that a liberal transfusion strategy is more effective in those with DCI at baseline. DCI is associated with anemia⁶. Transfusion in anemic patients with DCI is associated with less ischemic burden.²⁵⁻²⁸
- Baseline Radiographic Vasospasm: present at randomization vs not. We hypothesize that a liberal transfusion strategy is more effective in those with vasospasm at baseline. Vasospasm is associated with anemia⁶. Transfusion in anemic patients with vasospasm is associated with less ischemic burden.²⁵⁻²⁸

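### The SAP hypothesises effect modification in its subgroups but plans no treatment-by-subgroup contrast; the aneurysm-treatment subgroup also needs a time point and a place for unsecured patients

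*SAP*

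**What the plan says.** SAP 5.2 introduces the subgroups in one sentence: "We plan exploratory subgroup analyses for the primary outcome (as described above) in the following groups". Seven follow: age, sex, WFNS grade, modified Fisher grade, aneurysm treatment, baseline DCI and baseline vasospasm. Six carry a directional hypothesis. For aneurysm treatment, for example, it is that a "liberal transfusion strategy is more effective in those with extravascular interventions". For sex the hypothesis is no difference.

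The model that the sentence points back to is the binomial mixed model with log link, with treatment and sex as fixed terms and centre as a random one. Neither SAP 5.2 nor SAP Table 4 mentions an interaction term, a ratio of risk ratios or a heterogeneity test, and Table 4 has no subgroup row. SAP 3.1 adds: "A p-value will only be reported for the primary outcome".

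On timing, the DCI subgroup is tied to randomisation ("Baseline DCI: present at randomization vs not"), as is vasospasm, and the two grades are taken at admission. The aneurysm subgroup is given only as "Method of treatment of Aneurysm: neurosurgical (craniotomy) extravascular versus endovascular aneurysm intervention". Protocol Table 3A records a three-state baseline variable, "Clip or coil or not secured". SAP 4.3 lists "status of aneurysm and securing technique" among the baseline characteristics, and SAP Table 3 includes a row for no treatment. Protocol Table 3B logs later treatment separately, under "Definitive Aneurysm Management (if completed post randomization)".

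**The concern.** A statement that treatment works better in one level than in another concerns the difference between two effects. It is answered by estimating that difference, not by an effect estimate within each level. If only level-specific risk ratios with intervals are reported, readers will tend to compare an interval that excludes 1 with one that does not and read this as effect modification. The levels are much smaller than the trial, so such pairs arise often even when the effect is the same throughout.

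The aneurysm subgroup raises a second, smaller question. Treatment can be completed after randomisation, and the wording does not say whether a patient unsecured at randomisation is left out or classified by what was done later. Classification by a later event could be influenced by the allocated strategy.

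**Working it through.** **Inputs.** From the SAP: 40% vs 30% unfavourable outcome, 80% power, 5% type I error, 3% loss, total 740 (2.3); 1:1 allocation (2.2); two-sided 95% intervals (3.1). Assumed, because the documents give no subgroup shares: the smaller level holds 20% to 50% of patients, and each level has the overall event rates.

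**The plan's own figure.** Per arm, n = [1.960·√(2·0.35·0.65) + 0.842·√(0.40·0.60 + 0.30·0.70)]² / 0.10² = (1.322 + 0.565)² / 0.01, which gives 356, or 712 in total. Allowing for 3% loss, 712/0.97 gives 735 and 712 × 1.03 gives 734. The stated 740 is reproduced closely. Evaluable patients: 740 × 0.97 = 718, or 359 per arm; power is 80.3%.

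**Precision within a level.** With m patients per arm in a level, Var(log RR) = 0.60/(0.40m) + 0.70/(0.30m). Power for the interval to exclude 1 is Φ(|ln 0.75|/SE − 1.96), with |ln 0.75| = 0.288. The chance that exactly one of two levels excludes 1 is pA(1 − pB) + pB(1 − pA).

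| Split | SE of log RR (A, B) | Power (A, B) | Exactly one excludes 1 |
|---|---|---|---|
| 50:50 | 0.146, 0.146 | 50%, 50% | 50% |
| 30:70 | 0.189, 0.124 | 33%, 64% | 55% |
| 20:80 | 0.231, 0.116 | 24%, 70% | 61% |

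At 30:70 the expected results are 0.75 (0.52 to 1.09) and 0.75 (0.59 to 0.96): the same effect in both levels, but only one interval excludes 1.

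**Across seven subgroups.** All seven cut the same 718 patients, so the chances cannot be multiplied as if independent. In simulation with seven random equal two-level splits unrelated to outcome, at least one split is discordant in about 87% of trials at 40% vs 30%, about 63% at 40% vs 35%, and about 34% with no effect (repeat runs differ by a point or two). There is no effect modification in any of these scenarios.

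**What the contrast would deliver.** SE(log ratio of risk ratios) = √(SE_A² + SE_B²):
- 50:50: √(0.146² + 0.146²) = 0.207
- 20:80: √(0.231² + 0.116²) = 0.258

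These are 2.0 and 2.5 times the overall SE of 0.103. The 95% interval is the ratio multiplied and divided by exp(1.96 × SE), which is 1.50 to 1.66. The ratio detectable with 80% power is 0.56 to 0.49. Power for a true ratio of 0.75 is 29% to 20%.

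**Aneurysm classification.** Bias arises only if the allocated strategy shifts later treatment choice. An illustration with no true effect used assumed inputs: 5% to 30% unsecured at randomisation, and craniotomy use among severe unsecured patients differing between arms by 10 to 20 points. The spurious ratio was 0.996 to 0.951, and exactly 1.000 with no arm difference. None of these inputs is in the documents.

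**The case against.** The strongest reply is that the subgroups are labelled exploratory, that SAP 3.1 restricts p-values and works with intervals, and that no within-level significance claim is planned. All of this is true and limits the seriousness. It does not supply an estimate of the hypothesised quantity. The back-reference may also identify only the endpoint rather than the model; on that reading the subgroup method is unstated, and there is still no contrast.

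A reader might infer that the hypotheses cannot be judged at all. That goes too far. For a two-level subgroup an approximate ratio and interval can be worked out from two published risk ratios. This is outside the plan, and it is not straightforward for WFNS and modified Fisher, which have no stated cut-points. Nor would the added contrast settle the hypotheses, given its low power.

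A reader might multiply seven 50% chances and call a false contrast almost certain (1 − 0.5⁷ = 0.99). The splits share patients, so that figure is wrong, and the simulated 87% itself depends on the full design effect and on two-level equal splits.

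A reader might also infer that the aneurysm subgroup is defined by treatment given after randomisation and so breaks the randomised comparison. The documents do not show this. A three-state baseline variable exists, later treatment is logged separately, and nothing says that the later version will be used. Likewise, the no-treatment row stands in a baseline table, so it is not evidence of patients who were never secured.

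**Conclusion.** The point holds as an improvement to exploratory analyses. All seven subgroup hypotheses concern a contrast that the SAP does not plan to estimate. Under a uniform 40% vs 30% effect, a single two-level split gives discordant intervals in about 50% to 61% of trials for smaller-level shares of 50% down to 20%. Across seven equal splits the figure is about 87%, and it falls to 63% and 34% for a smaller effect and for none. These figures rest on assumed subgroup shares, common event rates across levels and, for the seven-split figures, splits unrelated to outcome.

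The aneurysm subgroup is secondary: its time point and the place of unsecured patients are unstated. The likely bias is small and cannot be quantified from the documents. The primary analysis is untouched.

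**What to change.** In SAP 5.2, and in a new row of Table 4, state that each subgroup is analysed in one model: the primary model plus the subgroup variable and its product with treatment. Report the level-specific risk ratios together with the ratio of risk ratios and its 95% interval, without significance claims. This agrees with SAP 3.1. Give the levels or cut-points to be used for WFNS and modified Fisher.

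For aneurysm treatment, state that the subgroup uses status at randomisation with three levels: clipped, endovascular, not secured.

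No new data are needed, and SAP 2.5 places publication of the SAP before database lock. The cost is a wording change and one further term per model. The intervals will be wide (the ratio multiplied and divided by about 1.5 to 1.7), and the not-secured level may be small.
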